9.6 Advised treatment off protocol

Note: This phase is not an official part of this protocol and contains only an advise for treatment.

For patients still in complete remission after completion of protocol treatment it is advised to continue with consolidation therapy and (if possible) stem cell transplantation. In patients who did not achieve CR, treatment with high dose Ara-C and mitoxantrone followed by (autologous or) allogeneic stem cell transplantation is advised.

Consolidation therapy may consist of a single course of HAM. The HAM protocol has to start within one month after the last alemtuzumab administration, preferably as soon as the leukocytes and thrombocytes have been recovered.

Agent	Dose/day	Route	Days
Ara-C	3 g/m ² , 3-hr infusion every 12 hrs	i.v.	1, 2, 3, 4
Mitoxantrone	10 mg/m², 30 min infusion	i.v.	3, 4, 5
MTX	15 mg	i.t.	1

In case a suitable stem cell donor is available, an allogeneic stem cell transplantation should be performed as soon as possible.

10 End of protocol treatment

Reasons for going off protocol treatment are:

- 1 Normal completion of protocol treatment
- 2 Progressive disease
- 3 No CR after induction cycle I
- 4 Relapse (bone marrow or extra-medullary)
- 5 Excessive extra-medullary drug toxicity
- 6 Death whatever the cause
- 7 No compliance of the patient (especially refusal to continue treatment)
- 8 Major protocol violation*
- 9 Delay or interruption of treatment, exceeding the limits (see paragraph 9)

* Major protocol violation defined as:

other ALL treatment given than as described in paragraph 9, or not meeting eligibility criteria for inclusion as described in paragraph 8.1.

11 Required clinical evaluations

11.1 Time of clinical evaluations

•	At entry:	baseline, at most 4 weeks before start of protocol treatment
•	After pre-phase:	determine corticosteroid sensitivity on day 8
•	After 8 study doses of	clinical evaluation and response assessment on day 18 of
	induction cycle I	induction cycle I or after 8 doses of alemtuzumab 30 mg (arm
		A) or 60 mg (arm B)
•	After induction cycles I and II	clinical evaluation and response assessment as soon as
		WBC > 1 x 10^{9} /l and platelets > 100 x 10^{9} /l, but in case of
		delayed hematopoietic recovery at last 14 days (induction
		cycle I) or 28 days (induction cycle II) after the last
		alemtuzumab administration
•	Follow up	clinical evaluation and response assessment every 6 months

11.2 Required investigations

	At entry	After Pre-	After 8 study	After Induction	After Induction	FU
		phase	doses	cycle I	cycle II	
Medical history	х	х	x	х	x	х
Physical examination	х	х	x	x	x	х
Hematology	х	х	x	x	x	х
PB immunophenotyping	х			х		x ¹⁾
PB PCR BCR/ABL	х			х		
PB storage	х		x ⁴⁾	x ⁴)	x ⁴⁾	
Blood chemistry	х	х	x	х	x	
Bone marrow aspirate						
Morphology	х		x	х	x	x ¹⁾
BM immunophenotyping	х			x ⁴⁾	x ⁴⁾	x ¹⁾
Cytogenetics	x ³⁾			x ⁴⁾	x ⁴⁾	
BM PCR BCR/ABL	х			x ⁴⁾	x ⁴⁾	x ¹⁾
BM storage	х		x ⁴⁾	x ⁴⁾	x ⁴⁾	
Specific investigations						
Chest x-ray	х					
ECG	х					
CSF examination	х			х		o.i.
EMD examination	o.i.	o.i.	0.i.	0.i.	o.i.	o.i.
Virological tests	х	o.i.	0.i.	0.i.	o.i.	o.i.
Microbiological tests	х	o.i.	o.i.	o.i.	o.i.	o.i.

- o.i. on indication
- 1) only on clinical and laboratory signs of relapse
- 2) at achievement of morphologic CR if aberrant karyotype at diagnosis
- 3) if data from initial diagnosis are not available
- 4) only at first achievement of complete remission

11.2.1 Medical history

Standard medical history, with special attention for:

- WHO performance status
- Adverse events
- Infections
- Bleeding
- Symptoms for CNS involvement
- Concomitant therapy

Only at entry:

- Prior and present other diseases
- Antecedent hematological or oncological diseases
- Previous chemotherapy or radiotherapy

11.2.2 Physical examination

Standard physical examination, with special attention for:

- Height (only at entry)
- Body weight
- Surface area
- Blood pressure
- Pulse
- Temperature (daily during induction treatment)
- Bleeding tendency
- Lymph node enlargement
- Liver and spleen size
- Any sign of possible extramedullary disease

11.2.3 Hematology

- Hemoglobin
- Hematocrit
- Reticulocytes
- Platelets
- WBC
- WBC differential
- Immunophenotyping (see 11.2.7)
- Molecular analysis (see 11.2.9)

11.2.4 Blood chemistry

- Urea
- Creatinin
- Total bilirubin
- AST (SGOT)
- ALT (SGPT)
- Alkaline phosphatase
- Gamma GT
- LDH
- Total proteins
- Albumin
- CRP
- Glucose
- Calcium
- Phosphate
- Sodium
- Potassium
- Uric acid

11.2.5 Bone marrow aspirate

- Morphology
- Immunophenotyping (see 11.2.7)
- Cytogenetic analysis (see 11.2.8)

• Molecular analysis (see 11.2.9)

11.2.6 Specific investigations

- X-Thorax
- ECG
- Cerebral spinal fluid examination
- Pathology of other suspected extramedullary disease
- Virological tests (including CMV)
- Microbiological tests

11.2.7 Immunophenotyping

Immunophenotyping of blood and bone marrow, including CD52, by flowcytometry will be performed at diagnosis of relapse in all patients. In virtually all cases the malignant lymphoblasts will express a phenotype that can be used for detection of minimal residual disease after treatment. Every time the bone marrow is examined, flowcytometry should be performed to quantitate the level of residual lymphoblast by a technique that is able to detect at least one malignant cell among 1,000 bone marrow cells.

Review by the HRC will be performed at diagnosis of relapse only (see 4.1).

11.2.8 Cytogenetic analysis

Conventional cytogenetic analysis on relapse material should be performed in patients from whom no cytogenetic data of initial diagnosis are available and in case of an aberrant karyotype repeated at the first achievement of morphologic CR. For Philadelphia chromosome positivity the detection of BCR/ABL will be required.

Central review will be performed for cytogenetic analysis as described in paragraph 4.2.

11.2.9 Molecular analysis

Blood and bone marrow cells should be investigated for BCR/ABL at entry in this study. In case of BCR/ABL positivity follow up investigations for BCR/ABL should be performed at all bone marrow examinations mentioned in this protocol.

Blood cells (30 ml of peripheral blood (in EDTA) for viable cryopreservation of 5 –10 ampoules with 10×10^6 nucleated blood cells each) and bone marrow cells (1 – 2 ml of bone marrow (preferable in citrate) for viable cryopreservation of 5 – 10 ampoules with 10×10^6 nucleated bone marrow cells each) should be stored in liquid nitrogen at entry of this study and after first achievement of a complete remission for further analysis in the future of minimal residual disease by using a PCR technique for Ig and TCR gene rearrangement as well as for leukemia-specific breakpoint fusion regions.

Diagnostic and follow-up samples should be sent to the local laboratory. If necessary this local laboratory will forward the samples to a central laboratory as agreed within the Network for Molecular Diagnostics.

11.2.10 Corticosteroid sensitivity

Corticosteroid sensitivity will be determined on day 8 of the pre-phase. Definition of corticosteroid-sensitivity: leukemic blasts $< 1 \times 10^{9}$ /l in the blood.

11.3 Response assessment

Response will be assessed after 8 days of the study dose. After remission induction cycles I and II, response will be assessed as soon as WBC > 1×10^{9} /I and platelets > 100×10^{9} /I, but within two weeks (induction cycle I) and/or 4 weeks (induction cycle II) of the last alemtuzumab administration, by evaluation of the bone marrow aspirate and blood according to the definitions described in appendix B.

During follow-up bone marrow examination will only be performed when relapse is suspected based on unexpected abnormalities of blood cell counts, appearance of circulating blasts, or clinical abnormalities originating in the CNS.

12 Toxicities

Toxicities will be scored according to the NCI Common Terminology Criteria for Adverse Events, CTCAE version 3.0, published December 12, 2003 (Appendix D).

12.1 Alemtuzumab

The most frequent adverse events are acute infusion related toxicity including rigors, fever, nausea and vomiting, hypotension, fatigue, rash, urticaria, dyspnoea, headache, pruritus and

diarrhea. The majority of these adverse events are mild to moderate in severity. According to the data in CLL patients the infusion related events decrease in incidence during the treatment, most striking after the first week of therapy. The most serious toxicity of alemtuzumab is infections. The reported opportunistic infections of grade 3 or 4 during the phase II studies are given in table 1. Most frequent infections reported are herpes simplex and pneumonia caused by *Pneumocystis carinii,* cytomegalovirus, *Aspergillus* and Herpes zoster. Mucormycosis infection is also reported but is uncommon.

Infection-site	Infections	
Pathogen	No	% of patients
Pneumonia	23	15.4
Bacterial	8	5.4
PCP	5	3.4
Fungal	4	2.7
Interstitial	2	1.3
Other	5	3.4
Sepsis/bacteremia	15	10.1
Line infection	8	5.4
Sepsis	7	4.7
Herpes infection	7	4.7
CMV	4	2.7
Herpes simplex	1	0.7
Herpes zoster	2	1.3

Table 1. Infections grade 3 or 4 reported during the phase II trials

Hematological toxicity is common but not too relevant for this study. Transient decrease in hemoglobin was observed during therapy. All patients developed lymphopenia. The total number of T-cells was intensively reduced. By the end of therapy T-cell recovery started to occur, regardless of the total cumulative dose of alemtuzumab given.

In phase II studies adverse events contributing to discontinuation of treatment were reported in 19-29% of CLL patients.

13 Reporting serious adverse events

13.1 Definitions

Adverse event (AE)

An adverse event (AE) is any untoward medical occurrence in a patient or clinical study subject during protocol treatment. An AE does not necessarily have a causal relationship with the treatment. An AE can therefore be any unfavorable and unintended sign (including an abnormal laboratory finding), symptom, or disease temporally associated with the use of a medicinal (investigational) product, whether or not related to the medicinal (investigational) product.

Adverse reaction (AR)

Adverse reactions (AR) are those AEs of which a reasonable causal relationship to any dose administered of the investigational medicinal product and the event is suspected.

Serious adverse event (SAE)

A serious adverse event is defined as any untoward medical occurrence that at any dose results in:

- death
- a life-threatening event (i.e. the patient was at immediate risk of death at the time the reaction was observed)
- hospitalization or prolongation of hospitalization
- significant / persistent disability
- a congenital anomaly / birth defect
- any other medically important condition (i.e. important adverse reactions that are not immediately life threatening or do not result in death or hospitalization but may jeopardize the patient or may require intervention to prevent one of the other outcomes listed above)

Note that ANY death, whether due to side effects of the treatment or due to progressive disease or due to other causes is considered as a serious adverse event.

Unexpected SAE

Unexpected Serious Adverse Events are those SAE's of which the nature or severity is not consistent with information in the relevant source documents. For a medicinal product not yet approved for marketing in a country, a company's Investigator's Brochure will serve as a source document in that country.

Suspected unexpected serious adverse reaction (SUSAR)

All suspected ARs which occur in the trial and that are both unexpected and serious.

Protocol treatment period

The protocol treatment period is defined as the period from the first study-related procedure until 30 days following the last dose of protocol treatment or until the start of another systemic anticancer treatment off protocol, if earlier.

13.2 Reporting of (serious) adverse events

Adverse event

AEs will be reported on the CRF. All adverse events of Grade 2 or higher, with the exception of progression of disease, occurring during the protocol treatment period will be reported. Adverse events occurring after that period should also be reported if considered related to protocol treatment.

SAE and Unexpected serious adverse event

All SAEs occurring during the protocol treatment period must be reported to the HOVON Data Center by fax **within 24 hours of the initial observation of the event**, except hospitalizations for:

- a standard procedure for protocol therapy administration. Hospitalization or prolonged hospitalization for a complication of therapy administration will be reported as a Serious Adverse Event.
- the administration of blood or platelet transfusion. Hospitalization or prolonged hospitalization for a complication of such transfusion remains a reportable serious adverse event.
- a procedure for protocol/disease-related investigations (e.g., surgery, scans, endoscopy, sampling for laboratory tests, bone marrow sampling). Hospitalization or prolonged hospitalization for a complication of such procedures remains a reportable serious adverse event.
- prolonged hospitalization for technical, practical, or social reasons, in absence of an adverse event.
- a procedure that is planned (i.e., planned prior to starting of treatment on study; must be documented in the CRF). Prolonged hospitalization for a complication considered to be at least possibly related to the protocol treatment remains a reportable serious adverse event.

All details should be documented on the **Serious Adverse Event and Death Report**. In circumstances where it is not possible to submit a complete report an initial report may be made giving only the mandatory information. Initial reports must be followed-up by a complete report

within a further 2 working days and sent to the HOVON Data Center. All SAE Reports must be dated and signed by the responsible investigator or one of his/her authorized staff members.

At any time after the protocol treatment period, *unexpected* Serious Adverse Events that are considered to be at least suspected to be related to protocol treatment must also be reported to the HOVON Data Center using the same procedure, **within 24 hours after the SAE was known to the investigator**.

The investigator will decide whether the serious adverse event is related to the treatment (i.e. unrelated, unlikely, possible, probable, definitely and not assessable) and the decision will be recorded on the serious adverse event form. The assessment of causality is made by the investigator using the following:

RELATIONSHIP	DESCRIPTION
UNRELATED	There is no evidence of any causal relationship to the protocol treatment (also
	include pre-existing conditions)
UNLIKELY	There is little evidence to suggest there is a causal relationship (e.g. the event did
	not occur within a reasonable time after administration of the trial medication).
	There is another reasonable explanation for the event (e.g. the patient's clinical
	condition, other concomitant treatments).
POSSIBLE	There is some evidence to suggest a causal relationship (e.g. because the event
	occurs within a reasonable time after administration of the trial medication).
	However, the influence of other factors may have contributed to the event (e.g. the
	patient's clinical condition, other concomitant treatments).
PROBABLE	There is evidence to suggest a causal relationship and the influence of other factors
	is unlikely.
DEFINITELY	There is clear evidence to suggest a causal relationship and other possible
	contributing factors can be ruled out.
NOT	There is insufficient or incomplete evidence to make a clinical judgement of the
ASSESSABLE	causal relationship.

13.3 Processing of serious adverse event reports

The HOVON Data Center will forward all reports within 24 hours of receipt to the study coordinator and the study central data manager. The report of an SAE will be the signal for the central data manager to ask the investigator or the responsible local data manager to complete

and send as soon as possible all relevant CRF's for the involved patient with details of treatment and outcome.

14 Endpoints

14.1 Primary endpoints

- Percentage of patients that reach a CR on induction cycle I in each arm.
- Percentage of patients with severe toxicity on induction cycle I in each arm.

14.2 Secondary endpoints

- Toxicity profile related to each treatment step and intervals between treatment steps.
- Event-free survival (i.e. time from registration until no CR on protocol, relapse or death, whichever comes first); Event-free survival for patients without a CR is set at one day.
- Disease-free survival (i.e. time from achievement of CR to date of relapse or death from any cause, whichever occurs first).
- Overall survival measured from time of registration.

15 Data collection

Data will be collected on Case Report Forms (CRF) to document eligibility, safety and efficacy parameters, compliance to treatment schedules and parameters necessary to evaluate the study endpoints. Data collected on the CRF are derived from the protocol and will include at least:

- inclusion and exclusion criteria
- baseline status of patient including medical history and stage of disease
- timing and dosage of protocol treatment
- adverse events
- parameters for response evaluation
- any other parameters necessary to evaluate the study endpoints
- survival status of patient
- reason for end of protocol treatment

Each CRF page will be identified by a pre-printed trial number, and a unique combination of patient study number (assigned at registration), hospital and patient namecode (as documented at registration) to be filled out before completing the form.

The CRF will be completed on site by the local investigator or an authorized staff member. Each page must be dated and signed by the local investigator upon completion. All CRF entries must be based on source documents. The CRF and written instructions for completing the CRF will be provided by the HOVON Data Center.

Copies of the CRF will be kept on site. The original CRF pages must be sent to the HOVON Data Center at the requested time points. How and when to send in forms is described in detail in the CRF header and the CRF instructions.

All data from the CRF will be entered into the study database by the HOVON Data Center.

16 Registration

Eligible patients should be registered and randomized before start of treatment. Patients can be registered at the HOVON Data Center of the Erasmus MC - Daniel den Hoed by phone call: [name] or [contact] Monday through Friday, from 09:00 to 17:00, or via the Internet through TOP (Trial Online Process; https://www.hdc.hovon.nl/top). A logon to TOP can be requested at the HOVON Data Center for participants.

The following information will be requested at registration:

- 1. Protocol number
- 2. Institution name
- 3. Name of caller/responsible investigator
- 4. Patient's initials or code
- 5. Patient's hospital record number (optional)
- 6. Sex
- 7. Date of birth
- 8. First or second relapse
- 9. Duration of last remission
- 10. Eligibility criteria

All eligibility criteria will be checked with a checklist.

Each patient will be given a unique patient study number. Patients will be randomized, stratified by institution, age (18-44 vs 45-59 vs 60-70), 1^{st} relapse vs 2^{nd} relapse, and duration of last remission (< 12 months vs \ge 12 months from achievement of last CR) with a minimization procedure, ensuring balance within each stratum and overall balance. Patient study number and result of randomization will be given immediately by TOP or phone and confirmed by fax or e-mail.

17 Statistical considerations

The aim of this study is to assess in adults of 18 - 70 years in 1st or 2nd relapse ALL, the response to and feasibility of alemtuzumab.

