This is a multicenter randomized phase II study. Relapsed ALL patients under the age of 71 years will be registered and randomized to receive prednisone and methotrexate in the pre-phase and thereafter two remission induction courses of alemtuzumab.

In addition to the more classical evaluation methods (morphology, immunophenotyping), the leukemic mass will be studied afterwards from stored blood and bone marrow samples by using the PCR technique for Ig and TCR gene rearrangement as well as for leukemia-specific breakpoint fusion regions at diagnosis and after achievement of first CR.

8 Study population

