9.1 Pre-phase

Agent	Dose/day	Route	Days
Prednisone	60 mg/m²,	p.o.	1-7
	divided in 2 daily doses		
MTX	15 mg	i.t.	on day 1 or at the time that most blast
			cells have disappeared from the blood

Blood morphology should be performed on day 8 to determine corticosteroid sensitivity

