9.2 Remission Induction cycle I

Study arm A

Agent	Dose/day	Route	Days
Alemtuzumab	3 mg	i.v.	8
Alemtuzumab	10 mg	i.v.	9
Alemtuzumab	30 mg	i.v.	10, 11, 12, 13, 14, 15, 16, 17,
			19, 21, 23, 26, 28, 30, 33, 35, 37, 40, 42, 44

Study Arm B

Agent	Dose/day	Route	Days
Alemtuzumab	3 mg	i.v.	8
Alemtuzumab	10 mg	i.v.	9
Alemtuzumab	60 mg	i.v.	10, 11, 12, 13, 14, 15, 16, 17,
			19, 21, 23, 26, 28, 30, 33, 35, 37, 40, 42, 44

See paragraph 9.5.2 for special management of alemtuzumab administration.

Response (see appendix B) will be evaluated on day 18 (or the day following 8 days of the study dose (30 mg or 60 mg)). Patients with progressive disease as measured after 8 days of the study dose (or at any time between that time point and the last alemtuzumab administration) will go off protocol treatment.

After induction cycle I response will be evaluated again as soon as WBC > 1×10^{9} /I and platelets > 100×10^{9} /I, or in case of delayed hematopoietic recovery at least within two weeks of the last alemtuzumab administration. Patients in complete remission (CR) will continue with remission induction cycle II, while all other patients will go off protocol treatment.

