These design parameters imply that in each treatment arm a maximum of 54 patients who started with induction cycle I will be assessed after induction cycle I for CR rate and severe toxicity, with an interim analysis after the first 24 patients, or as soon as 9 severe toxicities have been reported in the first 24 registered patients, whichever comes first:

- if after the first 24 patients in a treatment arm ≤ 5 CR's (20.8%) are observed, or if ≥ 9 severe toxicities (37.5%) are observed, that arm will be closed to further patient entry with the conclusion that the arm is not enough active or is too toxic, and should not be further investigated. Otherwise patient entry will be extended to 54 patients. However, when 24 patients have been randomized to each treatment arm, a maximum of 4 more patients may be randomized to each treatment arm before the randomization will be put on hold while awaiting the data for and results of the interim analysis.
- If after 54 patients in a treatment arm ≤ 14 CR's (14/54 = 25.9%, 95% CI = 15.0-39.7%) are observed, or if ≥ 18 severe toxicities (18/54 = 33.3%, 95% CI = 21.1-47.5%) are observed, the conclusion will be that the arm is not enough active or is too toxic, and should not be further investigated.
- Otherwise, the trial will conclude that the arm is active and feasible, and warrants further investigation in this patient population.

Since this design applies per treatment arm and does not take into account that the dose in arm B is higher than the dose in arm A, which implies that the true probability of severe toxicity in arm B is not smaller than in arm A and also that the true CR rate in arm B is not smaller than arm A, unless the latter could be explained by a high toxicity rate in arm B, the above stopping rules will be modified in the following way:

- if the observed toxicity rate in arm B is lower than in arm A, the average toxicity rate of both treatment arms will be used in the stopping/decision rules in both arms.
- If the observed CR rate in arm B is lower than in arm A, and this cannot be explained by a high toxicity rate in arm B, the average CR rate of both treatment arms will be used in the stopping/decision rules in both arms.

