Before the interim analysis, CR and toxicity data on induction cycle I will be actively requested for on a monthly basis. For this purpose a short questionnaire will be generated, which should be completed as soon as cycle I has been evaluated, or as soon as it has been decided that cycle I will not be administered at all. In order to overcome dropouts due to ineligibility, 120 patients will be randomized. With an expected accrual rate of 60 patients per year, entry will be completed in about 2-2.5 years, depending on the speed of initiation in each country.

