17.2 Analyses

All randomized patients, eligible and who started the induction treatment will be included in the analysis, according to the intention to treat.

Those patients who are not in CR within 2 weeks after induction cycle I will be considered as treatment failures.

The estimated CR rate after induction cycles 1 and 2 along with the 95% CI interval will be presented for each treatment arm.

The estimated severe toxicity rate (i.e. any side effect or infection of CTCAE grade 4) along with the 95% CI interval will be presented for each treatment arm.

The actuarial curves for EFS, DFS and OS will be computed using the Kaplan-Meier method and 95% CIs will be constructed.

Actuarial probabilities of relapse after CR or death in CR with corresponding standard errors will be calculated using the competing risk method.

In addition the analysis of toxicity will be done tabulation of the incidence of side effects and infections with CTCAE grade 2 or more (appendix D).

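### The dose arm is disclosed before a pre-phase common to both arms, yet only patients who later start cycle I count, so entry to the primary cohort can depend on the known dose

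*Protocol*

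**What the plan says.** Section 16 places randomisation ahead of all protocol treatment: "Eligible patients should be registered and randomized before start of treatment". Section 7 confirms that this means ahead of the pre-phase, since patients "will be registered and randomized to receive prednisone and methotrexate in the pre-phase and thereafter two remission induction courses of alemtuzumab". Section 16 also says when the arm becomes known: "Patient study number and result of randomization will be given immediately by TOP or phone and confirmed by fax or e-mail". No blinding is described.

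Section 9.1 gives one pre-phase regimen for everyone on days 1 to 7, followed by a blood reading: "Blood morphology should be performed on day 8 to determine corticosteroid sensitivity". In section 9.2 the alemtuzumab steps on days 8 and 9 are the same in both arms. The tables diverge only in the row for days "10, 11, 12, 13, 14, 15, 16, 17" and later, that is, from day 10. Under section 9.4, repeating a low-dose step moves the divergence later still.

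The decision rules in section 17.1 apply to "a maximum of 54 patients who started with induction cycle I will be assessed after induction cycle I for CR rate and severe toxicity". Section 17.2 uses the same restriction: "All randomized patients, eligible and who started the induction treatment will be included in the analysis, according to the intention to treat". Section 17.1 also expects some patients never to start, because the interim questionnaire is due once cycle I is evaluated or "as soon as it has been decided that cycle I will not be administered at all".

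**The concern.** For at least a week, including the day-8 blood reading, the site knows the dose, while membership of the primary cohort is still open. Section 5.6 describes the arm B dose as twice the CLL dose and cites infectious problems at 100 mg per day. It is therefore plausible that willingness to start a patient who has deteriorated during the pre-phase depends on the arm.

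If it does, the starters in A and B are no longer the comparable groups that randomisation produced. Two things are then at stake:

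- **Each arm's own verdict.** CR and toxicity are judged against fixed cut-offs. Leaving out poor-risk patients in one arm lowers that arm's toxicity rate and raises its CR rate.
- **The averaging rule in section 17.1.** It compares the observed rates in A and B on the premise that true toxicity and true CR are not smaller in B, which presumes that the arms differ only by dose. Different selection into the arms breaks that premise and can trigger averaging that changes the verdict in both.

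**Working it through.** **Inputs from section 17.1.** Unacceptable toxicity 40%, acceptable 20%; uninteresting CR 20%, target 40%; error limits 0.10 each. An arm passes toxicity with at most 8 of 24 and at most 17 of 54 events. It passes CR with at least 6 of 24 and at least 15 of 54. The total of 120 randomised for 2 × 54 = 108 assessed leaves 12, or 12/120 = 10%, which the plan assigns to ineligibility alone.

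**1. The plan's own design reproduces** (exact two-stage binomial, toxicity and CR independent, no averaging).
- Pass toxicity at 40%: 0.101; at 20%: 0.956.
- Pass CR at 20%: 0.088; at 40%: 0.947.
- Wrongly passing an inactive arm: 0.088 × 0.956 = 0.084.
- Wrongly passing a toxic arm: 0.101 × 0.947 = 0.096.
- Power: 0.947 × 0.956 = 0.905.

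All three meet the limits.

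**2. Effect of selective non-start on the rate among starters.** If a share f does not start and would have had event risk q:

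starter rate = (overall rate − f × q) / (1 − f)

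The protocol gives neither f nor q. I assume f = 0.10, borrowing the 10% above purely as a scale, and q = 0.60:

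(0.40 − 0.10 × 0.60) / 0.90 = 0.34 / 0.90 = 37.8%

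**3. One arm, averaging ignored.** The chance of passing the toxicity rule rises from 0.101 at 40% to 0.170 at 37.8%. With f = 0.05 and the same q it is 0.131. With f = 0.10 and q = 0.80 the starter rate is 0.32/0.90 = 35.6% and the chance 0.264. For CR at a true 20%, if 10% with a CR chance of 10% or 0% do not start, the starter rate is 21.1% or 22.2%, and the chance of passing rises from 0.088 to 0.125 or 0.171.

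**4. With the averaging rule.** If B's observed toxicity is below A's, the mean of the two is used in both arms. I applied this at 24 and at 54 per arm, with an arm passing when the count or the mean count is below 9 and below 18. Arm B's chance of passing the toxicity rule is:

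| True toxicity in A | B unselected (40%) | B selected (37.8%) |
|---|---|---|
| 40% | 0.03 | 0.06 |
| 30% | 0.08 | 0.14 |
| 20% | 0.10 | 0.17 |

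Averaging can only raise the rate applied to B here, so it dampens the bias. The damping is strong when A is as toxic as B and nearly absent when A is at 20%.

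**The case against.** Several counter-arguments have force.

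- **No between-arm test is planned.** Imbalance between the arms matters less than in a comparative trial. This stands, but the averaging rule does compare the arms, and each arm's rate is still exposed.
- **Dose-driven non-start is inferred.** The sentence in section 17.1 is about data collection, names no decision-maker, and would also cover death, refusal or ineligibility. The reasons for going off treatment in section 10 do not include investigator preference, the day-8 steroid reading does not gate cycle I, and the CRF records why treatment ended. A reader might infer that sites will select by dose. The documents show only that they could, with the arm known and no criteria attached to the decision.
- **The single-arm figures do not measure disclosure.** A reader might take 0.170, 0.264 or 0.125 to 0.171 as the damage done by early disclosure. They compare starters with all randomised patients. If the same patients were declined in both arms after a day-8 randomisation, the starter rate would still be 37.8% and the figure still 0.170. Disclosure accounts only for what differs between the arms. This objection stands in full.
- **Moving randomisation has consequences.** EFS and OS run from registration (section 14.2), so arm-specific curves would include about seven days before randomisation. The patient counts in section 17.1 would also need restating. Both belong in the amendment.

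**Conclusion.** The point holds as a weakness in when the allocation is revealed. The arm is known before a common pre-phase, the primary cohort is fixed after it, and nothing in the protocol stops the known dose from influencing who starts. This can bias the two arms' rates differently and undercuts the premise of the averaging rule.

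The size cannot be stated. The illustration (arm B's chance of passing the toxicity rule going from 0.03 to 0.06, 0.08 to 0.14, or 0.10 to 0.17, according to arm A's true rate) rests on an assumed 10% non-start, an assumed 60% toxicity risk in those patients, and selection in arm B only. Non-start unrelated to dose and prognosis causes no bias. The documents do not support the stronger claims that such selection is expected, or that the error rates inflate by the full single-arm amounts.

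The change is worth making because it is cheap and removes the arm-dependent part at source. All four stratification factors (institution, age, relapse number, duration of last remission) are available at registration, and the arms need not be told apart before day 10.

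**What to change.** Split section 16 into two steps in the existing online and telephone system:

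1. Register and check eligibility before the pre-phase.
2. Randomise, or at least disclose the arm, on day 8 after the blood reading, once it is confirmed that cycle I will start and immediately before the first alemtuzumab infusion.

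Amend sections 7, 16 and 17.1 to match. Count the 24 and 54 per arm from this randomisation and restate the 120. Set the time origin of arm-specific EFS and OS to randomisation. Report registered but not randomised patients separately, with reasons. State that the conclusions apply to patients who start cycle I, because the change removes selection that depends on the arm but not selection common to both arms.

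The cost is one extra entry or call per patient, a short amendment, and somewhat more registrations to reach the per-arm counts. Treatment, visits and tests are unchanged.
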